9.0 Confidentiality, Privacy and Data Management

9.1 Confidentiality

See the Research Data Plan Review Form

9.1.1 Identifiers associated with data and/or specimens

9.1.1.1 Use of Codes, Master List

9.1.2 Storage of Data and/or Specimens

9.1.3 Access to Data and/or Specimens

9.1.4 Transferring Data and/or Specimens

9.2 Subject Privacy

10.0 Data and Safety Monitoring Plan

10.1 Periodic evaluation of data

The study coordinator will be responsible for the daily oversight of subject safety. Research staff will assess for adverse events at each study visit and will make appropriate referrals to medical providers. [name], will meet regularly with the study staff to review participant's progress and their experiences with the tobacco products, including any adverse events. Entrance criteria will be reviewed following screening. Medical history will be reviewed by [name] for any contraindications for the treatment products and smoking behavior will be checked at each visit.

10.2 Data that are reviewed

Data that will be reviewed include:

- Accrual and retention
- Adverse events and serious adverse events
- Protocol deviations/violations
- Misconduct

- Conflict of interest
- Participants' ability to achieve study requirements
- Changes in cigarette consumption from baseline

10.3 Method of collection of safety information

All data, including safety data, will be coded directly into REDCap case report forms during study visits, over the phone or via online REDCap survey. Participant adverse events and serious adverse events will be assessed at each in-person study visit but can be reported at any time during the study.

10.4 Frequency of data collection

Safety data including adverse events and serious adverse events will be collected at each in-person visit. Cigarettes smoked per day will be collected regularly at in person visits.

10.5 Individuals reviewing the data

The study coordinator will be responsible for the daily oversight of subject safety. [name], will meet regularly with the study staff to review participants' progress and their experiences with the tobacco products, including any adverse events.

10.6 Frequency of review of cumulative data

Safety data will be reviewed cumulatively every six months by the principal investigator.

10.7 Statistical tests

Statistical methods will be used to analyze the safety data to determine whether harms are occurring. Paired sample t-test (or nonparametric Wilcoxon Rank-Sum test) will be used to examine the changes in cigarette consumption from the baseline. In addition, the point estimates and 95% confidence intervals for the accrual and retention-dropout rate, completion rate, and the proportions of adverse events and serious adverse events will be generated. The data will not be reviewed across treatment groups to maintain blinding; however, if the principal investigator perceives a need to assess safety based on an unblinded analysis, she can request this information and it will be provided.

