We currently know little about how neural activity and connectivity of the incentive salience and executive control circuitry change during cessation treatment. Given the advancements in pharmacotherapy and non-invasive brain stimulation techniques,^{30,31} gaining a nuanced understanding of how brain circuitry adapts during rehabilitation could identify neural targets for treatment. Verenicline and bupropion treatment are associated with reductions in neural activity throughout prefrontal brain circuitry during executive control and cue-reactivity tasks, respectively.^{32,33} However, given the reductions in dependence for the control groups, these neural changes were likely due to the effects of the medication, not changes in dependence.^{32,33} Very low nicotine content (VLNC) cigarettes have been used as an extinction-based cessation treatment to reduce the rewarding effects of cigarettes by significantly reducing nicotine delivery during smoking.^{6,34} Smokers rate de-nicotinized cigarettes as satisfying and trials of VLNC cigarettes result in decreases in the number of cigarettes smoked per day and self-reported dependence.³⁵ VLNC cigarettes provide a unique opportunity to assess changes in neural circuitry while smokers extinguish the association between nicotine and smoking stimuli and become less dependent on smoking without the confounding effects of nicotine replacement therapy or pharmacotherapy.

The current study will examine functional neuroadaptations in incentive salience and executive control circuitry while smokers switch to VLNC cigarettes over 6-weeks. Identifying brain circuitry that is

modified at various stages of recovery can lead to the development of targeted neuropharmacological cessation aids and brain stimulation techniques. The findings of the proposed study will characterize changes associated with the extinction of conditioned cues and reductions in dependence without the confounding effects of pharmacological aids. By measuring neural processes and connectivity among circuitry mid-intervention, the results of the proposed study will pinpoint aspects of neural circuitry that are sensitive to (or reflective of) early intervention effects.

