- The scans done during this study are NOT designed to detect or evaluate any medical condition. They are intended solely for research purposes. The investigators for this project are not trained to perform medical diagnosis, and the scans to be performed in the study are not optimized to find abnormalities. On occasion, a member of the research team may notice a finding on a scan that seems abnormal. When a finding is noticed, one of the investigators may consult a physician specialist, such as a radiologist or neurologist, as to whether the finding merits further investigation. If the specialist recommends further follow-up, the investigator or another member of the research team will contact the participant within **48 hours** of the recommendation and suggest that the participant contact his or her private medical provider for follow-up. To facilitate follow-up care, the participant may be given a copy of the images upon written request. Being told about a finding may cause the participant anxiety as well as suggest the need for additional tests and financial costs. Medical insurance may be affected whether or not the finding is ultimately proved to be of clinical significance. Costs for clinical follow-up will not be covered in the cost of research. Participants will be told that their decision as to whether to proceed with further examination or treatment is their own.
- Increased compensatory smoking: Compensatory smoking may lead to increased levels of toxicant exposure. In prior studies, compensatory smoking was minimal and higher levels of toxicant exposure were generally not observed. Cigarette consumption will be monitored throughout the 6-week randomization phase. Safety rules are in place to identify and remove participants who increase their smoking rate significantly.
- Nicotine withdrawal symptoms: Decreased nicotine cigarettes and abstaining from nicotine may result in nicotine withdrawal symptoms (e.g. irritability, anxiety, restlessness, depressed mood, increased appetite, fatigue, insomnia/sleep problems, impatience, headache, difficulty concentrating, frustration, anger, craving for sweets, constipation, coughing, dizziness, nausea and sore throat).

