16.2 Feasibility of recruiting the required number of subjects

The smoking prevalence in South Central Pennsylvania is 19% of the adult population and approximately 40% of these smokers have no current plan to reduce or quit smoking. Penn State has been conducting clinical trials of new tobacco products for four years and has amassed a database of thousands of smokers interested in research participation (Study# 0002213). With the use of this database we expect to recruit 90 subjects over four years.

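### Section 10.7 examines cigarette consumption only through a test of the mean change, without an interval or a count of increasers, so a flat or falling mean can hide a minority who smoke more

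*Combined protocol and SAP*

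**What the plan says.** Section 10.7 opens with its purpose: "Statistical methods will be used to analyze the safety data to determine whether harms are occurring". The one analysis it names for cigarette consumption is this: "Paired sample t-test (or nonparametric Wilcoxon Rank-Sum test) will be used to examine the changes in cigarette consumption from the baseline". It attaches no interval, margin, significance level or count of increasers to that test. The next sentence plans point estimates and 95% confidence intervals for accrual, retention, "completion rate, and the proportions of adverse events and serious adverse events will be generated". Change in consumption is not on that list, although Section 10.2 names it among the data reviewed.

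On timing, Section 10.6 says "Safety data will be reviewed cumulatively every six months by the principal investigator", and Section 16.2 says "we expect to recruit 90 subjects over four years". Section 8.1 expects 75 of about 90 to complete.

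On the harm, Section 11.0 names compensatory smoking and treats it person by person: "Safety rules are in place to identify and remove participants who increase their smoking rate significantly". Section 2.1 says that "trials of VLNC cigarettes result in decreases in the number of cigarettes smoked per day", and Section 2.2 cites the same direction for 0.4 mg cigarettes.

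Three other provisions bear on individual increases. Section 3.3.1 removes a participant whose average cigarettes per day (CPD) rises more than 100% above the baseline log. Sections 7.4.4 and 10.1 have logs and smoking behaviour checked at contacts and visits. Section 13.0 classes increased carbon monoxide and cigarette consumption as adverse events.

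**The concern.** A mean is a poor summary when the harm falls on some participants while most are expected to move the other way. Falls in the majority offset rises in the minority, and a larger sample does not cure this. The cancellation can occur within one arm, so it is separate from the pooling of arms that Section 10.7 adopts to keep the blind.

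A second, smaller problem is precision. Early cumulative reviews will hold few participants, and a p-value without an interval does not show how large a rise remains compatible with the data.

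At stake is what the principal investigator sees at a cumulative review. Rises that are real but short of a doubling may leave no visible trace in the consumption analysis. They would otherwise surface only through individual checks that Section 10.7 neither tabulates nor refers to.

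**Working it through.** **The plan's own figures.** Section 10.7 gives no power, margin or sample size. The only sample-size figures (28, 86 and 28 in Section 8.2) concern the main analysis. They reproduce with f = 0.25, 80% power, 5% type I error, three measurements and a within-person correlation of 0.5 (the last two are assumed), but they say nothing about the consumption test.

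**Step 1: participants per review.** Four years of six-monthly reviews gives 8. With even accrual, 90/8 = 11.25 and 75/8 = 9.4. The first four reviews then hold about 11, 22, 34 and 45 (counting all 90) or 9, 19, 28 and 38 (counting completers). The six-week lag is ignored, which slightly flatters the early counts.

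**Step 2: power for a uniform mean rise.** This assumes that the test is run at each review, two-sided at 5%; the documents state neither. The SD of the change is not given, so the rise is d SD units. Power = 1 − F(t₀.₉₇₅; n − 1, d√n), where F is the noncentral t distribution. The interval half-width is t₀.₉₇₅/√n.

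| Review | n | Miss rate, d = 0.5 | 95% half-width (SD) |
|---|---|---|---|
| 1 | 9–11 | 68–74% | 0.67–0.77 |
| 2 | 19–22 | 39–46% | 0.44–0.48 |
| 3 | 28–34 | 19–28% | 0.35–0.39 |
| 4 | 38–45 | 9–15% | 0.30–0.33 |
| Full | 75 | 1% | 0.23 |

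For d = 0.3, power is 12% at n = 9, 44% at n = 38 and 73% at n = 75. For d = 0.2, it is 40% even at n = 75. Over all eight reviews (completer counts), the chance of at least one significant rise is 99% for d = 0.5, 80% for 0.3 and 54% for 0.2, against 9% with no true change.

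**Step 3: masking at N = 75.** Let a fraction q change by u and the rest by v (both in % of baseline), with residual SD s of 20 to 30. All of these are assumptions; the documents give none. The mean change is qu + (1 − q)v, and the total SD is √[s² + q(1 − q)(u − v)²]. Significant results were counted by simulation.

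| Mix | Mean change | Total SD | Significant rise |
|---|---|---|---|
| 25% at +60, 75% at −20 | 15 − 15 = 0 | 40–46 | about 2% |
| 20% at +60, 80% at −10 | 12 − 8 = +4 | 34–41 | 12–15% |
| 20% at +60, 80% at −20 | 12 − 16 = −4 | 38–44 | 0.1–0.3% |
| 25% at +60, 75% at −10 | 15 − 7.5 = +7.5 | 36–43 | 31–41% |

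In the third mix the test shows a significant *fall* in 13–17% of runs, while one participant in five smokes 60% more. The fourth row shows the limit of the argument: with more increasers and a smaller fall in the rest, the mean begins to register the rise.

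**Step 4: sample size does not help.** Assume a baseline of 15 CPD, with 20% of participants rising by half (+7.5) and the rest falling by 2. The mean change is 0.2 × 7.5 − 0.8 × 2 = −0.1, and a significant rise appears about 2% of the time at n = 9, 38 and 75 alike (residual SD 4 to 8). If the rest do not change, the mean is +1.5 and the figure at n = 75 is 32–73%. So the masking depends on the others falling, which the protocol expects on the low-nicotine cigarette.

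**Step 5: what a count would show.** With 15 increasers among 75, the exact (Clopper–Pearson) result is 20%, 95% CI 12% to 31%. With none seen, the upper limit is 1 − 0.025^(1/n): 33.6% at n = 9, 9.3% at n = 38 and 4.8% at n = 75.

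**The case against.** The strongest reply is that the protocol does not leave rising consumption to the mean. Section 13.0 makes increased consumption an adverse event, and Section 10.7 reports adverse-event proportions with 95% intervals, so individual increasers have a route into a reported proportion. Section 3.3.1 removes those above a 100% rise, and logs are reviewed at contacts. Supply gives a further signal: at 125% of baseline, a six-week supply lasts someone at +60% about 6 × 1.25/1.6 = 4.7 weeks, so a participant using only study cigarettes would have to ask for more. This stands, and it rules out inferring that the mean test is the only check on rises short of a doubling. But Section 13.0 sets no threshold, the proportions are not broken out for consumption, and Section 10.7 refers to none of these provisions.

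A reader might also infer that a non-significant mean will be taken to show no harm. No passage says so; Section 10.7 says only that the test "will be used to examine the changes in cigarette consumption from the baseline". The weakness is that no reading rule is stated.

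Nor do the documents support the view that the reviews would usually miss a mean rise. At 0.5 SD that is true only of the first, and the reviews are cumulative and repeated. It holds for longer at smaller effects, but the documents give no SD or harmful margin with which to choose among them.

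Finally, the zero-mean mix yields about 2% by construction, and Section 11.0 reports that compensation was minimal in earlier studies. The mixes show what the test cannot see; they do not forecast what will happen.

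**Conclusion.** The point holds as a reporting gap in Section 10.7. The section sets out to determine whether harms are occurring, yet its only named consumption analysis is a test of the mean, without the interval that it plans for other quantities. In three of the four assumed mixes the test at N = 75 signals a rise in about 0.1–15% of runs; in the fourth it does so in 31–41%. These figures rest on assumed rises, falls and SDs. The early-review figures rest on even accrual and on the test being run at each review.

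The gap does not mean that rising consumption goes unmonitored. Nor do the documents make the six-monthly review the only route to suspension: Section 10.8 refers simply to review of the data, Sections 10.1 and 10.5 describe daily oversight and regular meetings, and Section 19.7 promises stopping rules. The improvement is worth making because it is cheap and addresses a risk that the protocol itself names.

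**What to change.** Amend Section 10.7 so that each cumulative review reports:

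- the mean change in cigarettes per day with its 95% confidence interval;
- the number and proportion of participants whose consumption rose beyond a reporting level set in advance by the sponsor, including those removed under Section 3.3.1, with an exact 95% interval;
- consumption-related adverse events as a separate line, with cross-references to Sections 3.3.1 and 13.0.

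Add a sentence that a non-significant or negative mean change is not by itself evidence of no harm. State whether participants removed for large increases stay in the mean, since dropping them would bias it downward. The reporting level is for tabulation only and leaves the removal rule unchanged.

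Two nearby items can be settled in the same edit. Section 3.3.1 announces more than one criterion for increased smoking but lists one, and this must be reconciled. The nonparametric test named in Section 10.7 is for independent samples; the signed-rank test is the paired counterpart.

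The cost is a few sentences and one extra table from cigarette logs already collected, with no new visits or participants. The downside is that intervals at early reviews will be wide and look less reassuring.

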7.4.3 Method for Assigning Subject to Treatment Groups

Participants will be randomized to one of two experimental conditions based on a blocked randomization sequence stratified by gender. A 2:1 randomization strategy will be used, resulting in 0.67 probability of being assigned to the very low nicotine cigarette, and a 0.33 probability of being assigned to the usual nicotine cigarette. The randomization key will be stored in REDCap and will be accessible only to unblinded study members and the faculty project mentor. The principal investigator will not have access to the code to ensure blinding.

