8.0 Subject Numbers and Statistical Plan

8.1 Number of Subjects

We expect to enroll approximately 90 participants in order to retain 75 study completers.

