8.2 Sample size determination

Dependent smokers of low SES (n=75) will be recruited for the current study through the TCORS study call center (protocol #2213). Two-thirds of the sample (n=50) will be randomized to the VLNC group to maximize power for the within-subjects repeated measures analyses while still allowing for an analysis of between-subjects effects. There is not currently an accepted method for determining sample size a priori for repeated measures fMRI designs. With repeated measures behavioral data, to detect a medium effect size ($f=0.25$) with 80% power and a Type I error rate of .05, a sample size of 28 is required to detect within-subjects effects, 86 for between-subject effects, and 28 for within x between interactions. The estimate for detecting such effects with fMRI is likely somewhat higher; however, my mentors have found within-subject effects with similar tasks that will be used for this project with comparable sample sizes; smoking cue reactivity (n=22)⁶¹ card-guessing task (n=44)⁵, and the n-back task (n=33)⁶². Thus, we estimate that the current design will have adequate power to detect small to medium within-subjects effects and medium to large between-subjects effects. The design will serve as pilot data to determine sample size for future studies. TCORS found retention rates of 85% for their 18-week trial and a prior 6-week VLNC intervention found retention rates at 92%.⁴⁹ Retention for the proposed study will likely be higher given frequent contact with participants (3-week visit and two phone-check-ins); however, with a conservative estimate of 80% retention and adequate compliance, the final sample size (n=60) would still be adequately powered. We will recruit until we have 75 study completers. It is likely that participants that complete informed consent at the remote screening will be ineligible. Therefore, we expect around 90 participants to complete informed consent and 75 to complete the entire study.

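### Section 10.7 names an independent-samples test (Wilcoxon rank-sum) as the alternative to a paired t-test; if used, it is over-conservative and loses power for small rises in cigarette consumption

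*Combined protocol and SAP*

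**What the plan says.** Section 10.7 of the combined protocol and SAP says that safety data will be tested for signs of harm. For consumption it specifies: "Paired sample t-test (or nonparametric Wilcoxon Rank-Sum test) will be used to examine the changes in cigarette consumption from the baseline". The same section adds that "The data will not be reviewed across treatment groups to maintain blinding", unless the principal investigator asks for an unblinded look. By default, then, this is a one-sample, within-person comparison on the pooled trial population.

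The section gives no significance level, no sidedness, no size of rise to be detected and no condition for moving from the t-test to the alternative. Section 10.6 sets a cumulative review every six months. Section 11.0 lists compensatory smoking among the additional risks and says: "Compensatory smoking may lead to increased levels of toxicant exposure".

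**The concern.** The rank-sum test treats baseline and follow-up values as two unrelated groups. It computes the variance of its statistic as if they were independent. When a heavy smoker at baseline tends to be a heavy smoker later, that variance is too large for the comparison being made. The test then rejects too rarely when nothing has changed and is insensitive to small real changes. The signed-rank test works on each person's difference and does not have this problem.

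The consumption comparison is the only hypothesis test that section 10.7 names. An analyst who followed the text literally, and judged the data unsuitable for a t-test, would run a test that does not match the design. The stake is the sensitivity of a pooled safety check, not a primary endpoint or any analysis in section 8.3.

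**Working it through.** **No plan figure to reproduce.** Section 10.7 gives no power or sample size. Section 8.2 states its criteria, "to detect a medium effect size ($f=0.25$) with 80% power and a Type I error rate of .05", for the behavioural repeated-measures calculation only. Two-sided 0.05 is therefore an assumption here.

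**Inputs from the documents**
- Target pairs, 75. Section 8.1: "We expect to enroll approximately 90 participants in order to retain 75 study completers".
- Conservative pairs, 60. Section 8.2: "with a conservative estimate of 80% retention and adequate compliance, the final sample size (n=60) would still be adequately powered".
- Early looks: 90 recruits over four years (16.2), reviewed every six months (10.6). That is 90/8 = 11.25 per interval, so about 11 at the first look and 22 at the second. This assumes even accrual, one pair per recruit and the test being run at each review.
- Pooling. Section 7.4.3: "A 2:1 randomization strategy will be used". A 0.5 SD rise confined to the larger arm becomes 0.5 x 50/75 = 0.33 SD in the pooled sample. Modest pooled shifts are therefore worth considering.

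**Assumed, because not stated:** bivariate normal data with equal SDs, correlation r of 0.5, 0.7 or 0.8, and a rise d in units of the cross-sectional SD.

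**Step 1: type I error of rank-sum on paired data.** Under no change its z statistic has SD s = sqrt(1 - rhoS), where rhoS = (6/pi) x arcsin(r/2).
- r = 0.5: rhoS = 0.483, s = 0.719, 1.96/s = 2.73, true size about 0.6%.
- r = 0.7: rhoS = 0.683, s = 0.563, 1.96/s = 3.48, true size about 0.05%.
- r = 0.8: rhoS = 0.786, s = 0.463, 1.96/s = 4.23, true size near 0%.

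Simulation gives about 0.5/0.1/0%, against a nominal 5%. Signed-rank stays at 4.4-5.8% in every setting tried.

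**Step 2: power, worked for 75 pairs and d = 0.2.**
- Rank-sum: mean z = d x sqrt(n/2) x sqrt(3/pi) = 0.2 x 6.124 x 0.977 = 1.197. Power = Phi((1.197 - 1.96)/s) = Phi(-1.06), Phi(-1.36), Phi(-1.65) = 14/9/5%.
- Signed-rank: mean z = [d/sqrt(2(1 - r))] x sqrt(n) x sqrt(3/pi) = 1.69, 2.19, 2.68. Power = Phi(mean z - 1.96) = 39/59/76%.

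**Step 3: simulated power at r = 0.5/0.7/0.8.** Repeat runs move single entries by up to about three percentage points.

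| Pairs | Rise (SD) | Rank-sum | Signed-rank |
|---|---|---|---|
| 75 | 0.2 | 15/8/5% | 38/59/75% |
| 60 | 0.3 | 29/29/23% | 61/84/94% |
| 22 | 0.5 | 30/29/26% | 57/80/93% |
| 60 to 75 | 0.5 | 82-98% overall | 96-100% overall |

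**Step 4: where rank-sum reaches 50% power.** The shift is about 1.96 x sqrt(2/n) x sqrt(pi/3), almost whatever the correlation. It is 0.33 SD at n = 75, 0.37 SD at n = 60, 0.60 SD at n = 22 and 0.86 SD at n = 11.

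**Step 5: range.** At r = 0 nothing is lost: with 60 pairs and 0.2 SD both tests have about 19% power. At r = 0.9 with 60 pairs and 0.3 SD, rank-sum has 18% and signed-rank 99.9%. Lognormal consumption gives a similar picture: 60 pairs and 0.3 SD on the log scale give rank-sum 30/26/24% and signed-rank 58/79/92%.

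**The case against.** A reader might infer that a real rise in smoking would usually be missed. The documents do not support that. They give no effect size, SD or correlation, and at the planned 60 to 75 pairs the rank-sum test usually detects rises above about 0.33-0.37 SD. At very small shifts or low correlation, the correct test would often miss the rise too.

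The loss is also conditional. The paired t-test comes first, and with 60 to 75 pairs it needs only the mean difference to be roughly normal. Skewness in consumption does not by itself force the alternative. The name sits beside a paired t-test and is probably a slip for signed-rank, which an analyst might well notice.

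A reader might also infer that the error gives false reassurance about the trial's main product risk. Section 11.0 does not rank its risks, and it reports that compensatory smoking was minimal in earlier studies. Other checks do not use this test: the individual removal criterion (3.3.1), the limit on extra supply (7.2.2), log and biomarker checks (7.4.4), review of consumption changes (10.2) and handling of increased exposure as an adverse event (13.0). No stopping rule hangs on the test, since 10.8 and 19.7 leave those rules to be developed.

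All of this stands, and it limits the severity. It does not rescue the wording. Rank-sum would suit a between-arm comparison of change scores, but the sentence concerns change from baseline and the default is no review by arm. No other section corrects it. The removal criterion applies to an individual rise of more than 100%, so it does not replace a check for a modest rise across the whole group.

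**Conclusion.** Wrong as written; minor severity. The named alternative does not fit the paired comparison. If it is used and the two measurements are positively correlated, it rejects in well under 1% of cases under no change at correlations of 0.5 or more. In the table's small-rise and early-look settings its power is between about one half and one fifteenth of that of the signed-rank test (29% against 61% at one end, 5% against 75% at the other). For a 0.5 SD rise at 60 to 75 pairs the practical loss is small.

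That the test is misnamed follows from the text alone. The size of the loss rests on the assumed correlation, distribution, shift and two-sided 0.05, and the early-look figures rest also on even accrual.

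**What to change.** In section 10.7, replace Wilcoxon rank-sum test with Wilcoxon signed-rank test. It would help to add the significance level and sidedness, and the condition under which the nonparametric test replaces the t-test. If an unblinded between-arm comparison is ever requested, describe that test separately.

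The necessary change is a single term. It needs no new data, visits or participants and does not touch the efficacy analyses.

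### Section 10.7 reviews safety only with the arms combined, which can dilute or mask a rise in smoking in one arm, and its only arm-level route unblinds the principal investigator

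*Combined protocol and SAP*

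**What the plan says.** Section 10.7 presents its methods as the means of finding out whether participants are being harmed. For smoking, "Paired sample t-test (or nonparametric Wilcoxon Rank-Sum test) will be used to examine the changes in cigarette consumption from the baseline". For AEs and SAEs there are point estimates with 95% confidence intervals: "the proportions of adverse events and serious adverse events will be generated". It then states that "The data will not be reviewed across treatment groups to maintain blinding". The one exception applies if the principal investigator judges that an unblinded safety analysis is needed: "she can request this information and it will be provided".

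Section 10.6 names the reviewer: "Safety data will be reviewed cumulatively every six months by the principal investigator". Section 20.1.2 also gives the principal investigator the monitoring of participant safety. No independent monitor is named.

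Section 7.4.3 says of the randomization key that it "will be accessible only to unblinded study members and the faculty project mentor", and adds: "The principal investigator will not have access to the code to ensure blinding". Section 7.1 keeps participants and study staff blind until the study ends. No section gives the mentor or an unblinded team member a safety review by arm, and no end-of-study safety analysis by arm is described.

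**The concern.** There are two linked problems.

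First, a change-from-baseline test that ignores arm answers a question about the average participant. The protocol's own background (section 2.1) expects cigarettes per day (CPD) to fall on VLNC cigarettes. That fall offsets any rise in the NNC arm, and the 2:1 ratio gives it double weight. Section 11.0 names compensatory smoking as a risk, and pooling also weakens its detection, though less. An AE imbalance between arms is averaged into one overall proportion.

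Second, the exception in 10.7 depends on the principal investigator seeing a reason for concern in combined data, which may hide that reason. If it is used, the cumulative safety reviewer and study lead learns the results by arm while the trial is running. Section 7.4.3 withholds the code from that person in order to protect the blind.

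**Working it through.** **Inputs from the documents.** Allocation is 2:1 (7.4.3), with 50 VLNC and 25 NNC completers (7.1). Review is six-monthly (10.6). Recruitment is 90 over four years (16.2), to reach 75 completers (8.1). The documents give no figure for the power of the safety tests and no SD for change in CPD.

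**Assumptions.** The within-arm SD of CPD change is 6, with 4 and 8 as a range. Tests are two-sided at 0.05. The shifts are illustrative.

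**Is the test pooled?** Section 10.7 does not use the word. But a paired comparison with baseline, made without looking by arm, has to combine the arms. The rank-sum alternative is a two-sample test by name. It is offered as a substitute for the paired t-test, so it does not signal an arm comparison.

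**Dilution.** Pooled mean change = (50 × VLNC + 25 × NNC)/75 = (2 × VLNC + NNC)/3.
- NNC +4, VLNC 0: 4/3 = 1.33, one third of the rise.
- NNC +4, VLNC −2: (−4 + 4)/3 = 0, fully masked.
- VLNC +3, NNC 0: 6/3 = 2, two thirds of the rise.

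**Pooled SD.** A difference D between the arm means also inflates the SD used in the test: √(6² + (2/3)(1/3)D²).
- D = 6: √(36 + 8) = 6.63.
- D = 4: √(36 + 3.56) = 6.29.
- D = 3: √(36 + 2) = 6.16.

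**Signal-to-noise at SD 6.**
- NNC +4, VLNC 0, pooled: 1.33/(6.29/√75) = 1.84. NNC arm alone: 4/(6/√25) = 3.33.
- VLNC +3, NNC 0, pooled: 2/(6.16/√75) = 2.81. VLNC arm alone: 3/(6/√50) = 3.54.

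**Probability of flagging a rise.** Pooled values come from 100,000 simulated trials per case. Arm values come from the noncentral t distribution.

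| VLNC, NNC shift | Pooled, SD 4 / 6 / 8 | Affected arm alone, SD 4 / 6 / 8 |
|---|---|---|
| −2, +4 | 1% / 2% / 2% | 99.8% / 89% / 67% |
| 0, +4 | 75% / 44% / 28% | 99.8% / 89% / 67% |
| +3, 0 | 98% / 80% / 56% | about 100% / 93% / 74% |

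**At interim reviews.** With even recruitment, 75 completers over eight half-years is 75/8 = 9.4 per review, of whom about 3 are NNC. At SD 6, the NNC-arm test of a +4 rise has power of about 11% with 3 participants, 27% with 6 and 56% with 12 (roughly two years in). It reaches 89% only with all 25. With 25 VLNC and 12 NNC and the opposing shifts, the pooled test flags a rise in about 1% of trials.

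**Adverse events.** The overall proportion is (2 × VLNC + NNC)/3. Proportions cannot be negative, so nothing cancels, but a difference disappears from view. For illustration, 15/50 against 0/25 would appear only as 15/75 = 20% (95% CI 12% to 31%). A Fisher exact test by arm gives p = 0.0015.

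**The case against.** Several points on the other side stand.

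- **Individual safeguards go beyond one removal rule.** Section 3.3.1 removes a participant whose average CPD rises by more than 100%. Section 7.2.2 limits resupply, 10.1 checks smoking at each visit, 13.0 treats increased CO and consumption as an AE, and 19.6 allows individual unblinding. None depends on the pooled mean. But they act on single participants, and would not show a moderate average rise or an AE imbalance in one arm.
- **The starkest contrast is selective.** It needs opposing shifts and full enrolment. No passage suggests that NNC cigarettes raise CPD by 4, and 11.0 calls compensatory smoking minimal in earlier studies. If compensation occurs in the VLNC arm and NNC stays flat, the loss is modest. A reader might infer that the planned test cannot answer the safety question at all. The 80% against 93% case does not support that.
- **AE proportions are not tested.** A reader might infer that AE signals cancel like CPD changes. Section 10.7 only estimates those proportions, so the problem there is dilution.
- **The conflict is with purpose.** A reader might infer that 10.7 flatly contradicts 7.4.3. Section 7.4.3 withholds the participant-level code, while 10.7 makes a conditional exception for a safety analysis, and an arm-level summary is not the code. Section 19.6 also leaves room for further unblinding guidelines, and 20.1.2 allows consultation with mentors. What remains is that the only arm-level route written down unblinds the person whom 7.4.3 keeps blind.
- **Routine arm-level CPD tables have a price.** CPD is a dependence outcome under Aim 3, and change in dependence is a primary endpoint (1.2). Repeated comparative looks need a reason.

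**Conclusion.** The point holds in a limited form. The 10.7 review can dilute an NNC rise to one third, or miss it when VLNC falls as expected, and it does not show AE differences between arms. At SD 6 and full enrolment, detection is about 2% against 89% with opposing shifts, 44% against 89% when only NNC rises by 4, and 80% against 93% when only VLNC rises by 3. The SD and shifts are assumptions. Arm-level review would be weak in the first year or more, so the figures describe the end of the trial and should not be read as an early-warning gain.

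The clearer defect is the route. Arm-level results would go to the principal investigator, against the purpose of 7.4.3 and the staff blinding in 7.1, although others already have access to the key. The change is worth considering. The documents do not show that participants are left unprotected.

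**What to change.** Reconcile 10.7 with 7.4.3. In 10.7, replace the words "she can request this information and it will be provided" with a request that goes to the faculty project mentor. The existing unblinded study member prepares AE/SAE and CPD tables by arm for the mentor, who tells the principal investigator only whether action is needed. AE/SAE tables by arm can go to the mentor at each six-monthly review. Routine six-monthly CPD tables by arm are more debatable, because CPD is also an outcome, and can be kept for when a request is made. The principal investigator keeps the combined tables, and individual unblinding under 19.6 is unaffected. Coded arm labels would not be enough, because the 2:1 group sizes identify the arms.

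The cost is a few sentences of protocol text and a short table from people who already have access to the key. The downside is that the mentor sees arm-level data, including CPD on request, during the trial. The mentor should therefore take no part in outcome assessment, and each look should be documented. The documents do not establish the mentor's independence or safety-monitoring experience, so the protocol should address both.
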